#### Operating characteristics

		Stop if $\text{Prob}\{\text{TOX} > 0.30 \mid \text{data}\} > 0.95$ $\text{Or Prob}\{\text{Response} < 0.33 \mid \text{data}\} > 0.975$	
True Toxicity Rate	True Response Rate	$\text{Pr}(\text{stop early})$	Median (25 th %ile, 75 th %ile)
0.10	0.15	0.81	30 (20, 40)
0.20	0.15	0.82	30 (20, 40)
0.30	0.15	0.84	30 (20, 30)

0.40	0.15	0.91	20 (10, 30)
0.50	0.15	0.98	20 (10, 20)
0.10	0.25	0.28	50 (40, 50)
0.20	0.25	0.28	50 (40, 50)
0.30	0.25	0.36	50 (30, 50)
0.40	0.25	0.64	30 (20, 50)
0.50	0.25	0.92	20 (10, 30)
0.10	0.33	0.06	50 (50, 50)
0.20	0.33	0.07	50 (50, 50)
0.30	0.33	0.17	50 (50, 50)
0.40	0.33	0.54	40 (20, 50)
0.50	0.33	0.90	20 (10, 30)
0.10	0.45	0.004	50 (50, 50)
0.20	0.45	0.01	50 (50, 50)
0.30	0.45	0.12	50 (50, 50)
0.40	0.45	0.51	40 (20, 50)
0.50	0.45	0.89	20 (10, 30)
0.10	0.55	0.001	50 (50, 50)
0.20	0.55	0.01	50 (50, 50)
0.30	0.55	0.12	50 (50, 50)
0.40	0.55	0.51	40 (20, 50)
0.50	0.55	0.89	20 (10, 30)

**E. Analysis Plan**

Patients' baseline ED levels will be reported along with the proportion for patients who improve by at least 1 level according to the IIEF-5 for each time point measured. The proportion will be reported along with a 95% credible interval implementing a non-informative prior of beta(0.33, 0.67). Additionally, the proportion of patients who ever improve by at least 1 level will be reported overall. For secondary measures, the safety profile of the PAVE combination will be reported overall and for each planned subgroup based on prior statin treatment, with adverse events summarized by grade and time to onset to first grade 3 adverse event. Finally, the number of patients who drop out of the study to start an ED prescription medication will be reported. Exploratory analyses will be utilized to determine whether baseline patient features can predict response to PAVE or adverse events.

The Investigator is responsible for completing an efficacy/safety summary report, and submitting it to the IND Office Medical Affairs and Safety Group, for review and approval. This should be submitted every 10 evaluable patients, complete 8 weeks of study treatment until enrollment is complete

A copy of the summary should be placed in the Investigator's Regulatory Binder under "sponsor correspondence".

Important medical events as defined above, may also be considered serious adverse events. Any important medical event can and should be reported as an SAE if deemed appropriate by the Principal Investigator or the IND Sponsor, IND Office.

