### **3.0 Objectives**

A. **Primary Objective:** To estimate the proportion of patients who achieve a clinically significant improvement in erectile dysfunction (ED) when treated with a combination of Atorvastatin or patient's currently prescribed statin, Vitamin E, and Pentoxifylline (PAVE). Clinically significant improvement is defined as an improvement by one category, e.g., from mild-moderate to mild, on the IIEF-5 [International Index of Erectile Function] score, in men with established ED who have completed radiation therapy for prostate adenocarcinoma.

B. **Secondary Objectives**

- i. To report the safety profile of PAVE.
- ii. To report the rate of choosing other ED treatments after PAVE.

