### **4.0 Patient Selection**

**Subject Inclusion Criteria:**

1. Histologically or cytologically confirmed diagnosis of adenocarcinoma of the prostate
2. Previous radiation therapy (any form) with curative intent for prostate cancer
3. Erectile dysfunction, as determined by an IIEF-5 score of <22
4. Normal testosterone (including men on testosterone replacement), defined as testosterone >150 ng/dl at the time of screening
5. Age  $\geq$ 18 years

6. Karnofsky Performance Status (KPS)  $\geq 70$ , or ECOG 0-2
7. Patients may be taking an HMG-coA-reductase inhibitor
8. Serum alanine aminotransferase (ALT) and aspartate aminotransferase (AST)  $\leq 3X$  upper limits of normal (ULN)
9. Creatinine Kinase  $< 5$  times ULN.
10. Normal renal function as defined below:

Normal renal function is defined as creatinine clearance  $\geq 30$  ml/min via the Cockcroft Gault Formula:

$$\text{Female CrCl} = \frac{(140 - \text{age in years}) \times \text{weight in kg} \times 0.85}{72 \times \text{serum creatinine in mg/dL}}$$

$$\text{Male CrCl} = \frac{(140 - \text{age in years}) \times \text{weight in kg} \times 1.00}{72 \times \text{serum creatinine in mg/dL}}$$

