## **5.0 Pre-treatment evaluation**

(must be completed within 8 weeks prior to the completion of second step enrollment in CORe; In the event that a patient cannot be seen in person to consent and is consented remotely, physical exam and vitals are not required prior to enrollment. KPS/ECOG maybe conducted from the telephone calls. Baseline labs could be drawn at outside facility and IIEF-5 questionnaire can be completed at home and both can be submitted via secure email or fax.)

A. History and Physical, including KPS or ECOG. Include the following information at a minimum:

1. Age
2. Race and ethnicity
3. T-stage, N-stage, M-stage, Gleason score, initial PSA, PSA prior to radiation
4. Radiation therapy details:

- a. treatment dates
- b. modality: protons, photons, brachytherapy (include isotope used and dose), or any combination of these modalities
- c. for external beam (photon, proton, or combination):
  - 1. include whether or not pelvic lymph nodes were treated, and if so, report total and daily dose/fraction
  - 2. report total dose and dose per fraction for treatment to prostate +/- seminal vesicles
- 5. Most recent androgen deprivation therapy: report dates of treatment and drugs used
- 6. smoking history
- 7. alcohol history
- 8. current medications including non-prescription substances will be recorded in the medical chart.
- 9. Most recent treatment tried for ED
- 10. complete past medical history including history or presence of diabetes mellitus, hypertension, hyperlipidemias, endocrinopathies, cardiovascular diseases (e.g., coronary artery disease, CVA, TIA), hematologic diseases and psychiatric conditions will be recorded in the medical chart.
- 11. history of prior abdominal &/or pelvic surgery
- 12. current relationship status (i.e., married, widowed, divorced, presence of significant other)

B. Baseline assessment of erectile function using IIEF-5.

C. Laboratory studies: serum testosterone, CK, liver panel, BUN, Creatinine, GFR estimation, CBC, INR, PT, PTT

D. Baseline CTCAE V4.03 items grade 2 or higher: blurry vision, abdominal distension, abdominal pain, bloating, diarrhea, dyspepsia, flatulence, gastrointestinal pain, nausea, vomiting, malaise, pharyngitis, urinary tract infection, bruising, arthralgias, bone pain, generalized muscle weakness, myalgia, headache, rash (maculopapular), flushing

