## **7.0 Drug therapy**

A. The HMG-coA reductase inhibitor used in this study will be Atorvastatin for patients not already on a different statin

B. Dosage: 10-80 mg PO once daily

1. Those patients not currently on a statin will receive 10 mg/d Atorvastatin
2. For those currently on a statin, the statin and dose will be maintained at the current dose, unless a change is indicated for management of hyperlipidemia.

[figure not shown]
- a. If patients in this category are not taking at least a moderate intensity LDL lowering regimen, as defined in Appendix F, the prescribing physician

will be contacted for permission to modify the drug regimen, and if permission is granted, the regimen will be modified accordingly.

- C. Vitamin E: 1000 international units PO once daily
- D. Pentoxifylline: 400mg PO three times per day
- E. Patients or their third party payers will be expected to cover the cost of the drugs.
- F. Medication intake will be annotated in a pill diary as noted in the corresponding

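### Does the plan need to commit to reporting response, as well as safety, by prior statin use?

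*Combined protocol and SAP*

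**What the plan says.** Section 3.0 A defines one pooled primary question: the proportion of men whose IIEF-5 score improves by at least one category on the combination, whether the statin is newly started or already prescribed. Entry is open to both kinds of patient (Section 4.0, inclusion criterion 7: "Patients may be taking an HMG-coA-reductase inhibitor"). Under Section 7.0 B, men not on a statin are started on atorvastatin. For men already on one, "the statin and dose will be maintained at the current dose, unless a change is indicated for management of hyperlipidemia". The trial summary (Section 1.0) gives each man's own baseline as the control.

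Sections 1.0 and 11.0 A name three groups by statin use at enrolment. The 2021 revision in 11.0 A replaced 270 patients, 90 per cohort, with 50 in total, and sets no number for any group.

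Section 11.0 E reports response at each measured time point with a 95% credible interval, and then: "Additionally, the proportion of patients who ever improve by at least 1 level will be reported overall". For safety it goes further: "the safety profile of the PAVE combination will be reported overall and for each planned subgroup based on prior statin treatment". It also states: "Exploratory analyses will be utilized to determine whether baseline patient features can predict response to PAVE or adverse events". Section 11.0 D allows the stopping rules to be applied to a single subgroup if toxicity or efficacy is seen to differ between groups.

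**The concern.** Within one paragraph of 11.0 E, safety is promised by statin group and response is not. The plan's own design makes response the outcome for which the split seems more natural. With each man as his own control, the baseline of a man already on a statin includes whatever that drug does for him, and only vitamin E and pentoxifylline are normally new. A man not on a statin has all three drugs ahead of him. Section 2.0 cites a gain of 3.4 IIEF points from statins in erectile dysfunction not caused by radiation, so a difference in response between the groups is plausible.

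If there is one, the pooled proportion is a weighted average whose weights are left to accrual. The same 16 responders out of 50 could come from two very different groups or from two identical ones, and the response results promised in 11.0 E would look the same. A reader wanting to apply the result to men already on a statin, or to men not on one, could be misled.

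**Working it through.** **Inputs.** N = 50 and the beta(0.33, 0.67) prior come from Section 11.0 C, and the 33% reference rate from 11.0 D. The documents give no response rates or sizes for the statin groups, so every split and group rate below is an assumption.

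**1. The plan's own figures.** With x responders among n men, the posterior is Beta(0.33 + x, 0.67 + n - x), and the interval runs between its 2.5% and 97.5% points.
- 16/50: Beta(16.33, 34.67) gives 20.1% to 45.3%, width 25.2 points.
- 17/50: Beta(17.33, 33.67) gives 21.8% to 47.4%, width 25.6 points.

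Both match 11.0 C and meet its target of less than 26 points. The stopping limits in 11.0 D also reproduce: toxicity 6/10/14/17 and response 0/2/5/7 at 10/20/30/40 patients. All of these refer to the pooled group.

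**2. How far accrual can move the pooled rate.** With a share w of men on a statin, pooled rate = w × (rate on statin) + (1 - w) × (rate not on statin).

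| Assumed rate, no statin / statin | w = 0.3 | w = 0.5 | w = 0.7 | Shift |
|---|---|---|---|---|
| 33% / 33% | 33.0% | 33.0% | 33.0% | 0 points |
| 35% / 30% | 33.5% | 32.5% | 31.5% | 2 points |
| 40% / 25% | 35.5% | 32.5% | 29.5% | 6 points |
| 45% / 20% | 37.5% | 32.5% | 27.5% | 10 points |

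For example, 0.3 × 25% + 0.7 × 40% = 35.5%. The dependence on mix is real where rates differ, but even the widest assumed gap shifts the pooled rate by less than half the interval width of about 25 points.

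**3. What a response table by statin group could show.** Take 16/50 with an assumed 25 men on a statin and 25 not.
- Unequal: 11/25, Beta(11.33, 14.67), gives 25.5% to 62.6%; 5/25, Beta(5.33, 20.67), gives 7.6% to 37.6%. The difference in posterior means is 6/26 = 23.1 points. Its 95% credible interval, from independent posteriors by numerical integration, is -1.5 to +46.6 points.
- Equal: 8/25 in each, Beta(8.33, 17.67), gives 15.9% to 50.8%.
- Near-equal thirds, for example 6/17: 15.6% to 57.9%, width 42 points.

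So even an observed gap of 44% against 20% leaves an interval that includes zero, and with three groups the intervals are wider still.

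**4. What the text already covers.** The sentence before the one quoted reports improvement time point by time point. Read in sequence, the word overall most naturally means at any time on trial rather than without subgroups. On either reading, 11.0 E contains no explicit promise of response by statin group. But adverse events summarised by statin group would normally carry the number of men in each, so the achieved mix should be visible. The exploratory analysis covers baseline predictors of response, and statin status at enrolment is a baseline feature that the plan itself singles out. Section 11.0 D presupposes that someone compares efficacy between the groups.

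**The case for a change.** The strongest case for a change is that it would be cheap. Response and statin group are both needed for 11.0 E anyway, so the table needs no extra patients or visits. Stating it in advance, with the same prior and a warning against causal reading, would also guard against a selective subgroup claim later. Small numbers are no reason to leave it out when safety is already split by the same small groups. The optional wording in 11.0 D and the unnamed features in 11.0 E show an intention to look, not a promise to report.

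Much of that stands: the explicit promise is absent, and the table would be harmless if labelled descriptive. What does not stand is that the plan falls short without it. The table would leave the primary estimate, its interval and every stopping decision as they are. The chance of stopping for futility also moves with the mix if rates differ, but that comes from pooled monitoring, which a table does not alter. Nor would it separate the statin's contribution. The groups form themselves and may well differ in the history recorded at entry (Section 5.0 A.10: "complete past medical history including history or presence of diabetes mellitus, hypertension, hyperlipidemias"). No minimum duration of statin use is set, and some regimens may be changed under Section 7.0 B. A difference, if seen, could have several explanations that the trial cannot tell apart.

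**Conclusion.** No change to the plan follows. Carried out as written, it gives a sound answer to the pooled question it declares, with the stated precision of 25 to 26 points at about 33%, and no figure or rule in it is wrong. What remains is silence on one descriptive breakdown. The exploratory analysis and the by-group safety report already point to it, and an analyst would be expected to supply it with group sizes and intervals.

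The expected gain is small. Under the assumed group rates, the mix moves the pooled result by 0 to 10 points, well inside its interval. An assumed 24-point gap between two groups of 25 would still have an interval that includes zero. This rests on the pooled proportion remaining the primary aim. A trial meant to compare men on and off a statin would need more than a table, and the 2021 revision gave up the 90 per cohort that might have served that purpose.

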**G. Modification of drug dosing where side effect can't be attributed to one specific drug:**

1. Since the 3 study drugs have overlapping toxicities, circumstances may arise in which it is not clear which drug is responsible for the toxicity.
2. If the toxicities are  $\geq$ Grade 3, stop all 3 drugs and the patient should be removed from the study.
3. If toxicity is Grade 2, first reduce the dose of atorvastatin as per guidelines above. If after 1 week the toxicity has not decreased to Grade 1 or resolved, reduce the dose of Pentoxifylline as per guidelines above. If after an additional week the toxicity has not decreased to Grade 1 or resolved, reduce the dose of Vitamin E as per guidelines above. If after another week the toxicity has not resolved or decreased to Grade 1, all 3 drugs should be stopped and the patient should be removed from the study.

4. Cardiovascular issues: for toxicity of Grade 3 or higher, all 3 drugs will be discontinued, and the patient directed to the nearest emergency department for urgent evaluation. For toxicity of Grade 2, guidelines delineated in sections 8.G.1-3 above will be followed for drug dosing modifications, while concurrently obtaining a cardiovascular evaluation from the patient's cardiologist (if he has one), or his personal primary care physician. At the patient's preference, cardiology evaluation may be obtained at MD Anderson. Continuation on study medications will be contingent on cardiology approval.

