**11.0 Biostatistics**

**A. Goal:**

The purpose of this trial and design is to provide inexpensive treatment for ED following XRT. While we hypothesize a smaller success rate than prescription ED treatments, this combination may be a less expensive alternative for those patients who do benefit. Three planned subgroups

will be enrolled, patients who are not on any statins at the time of enrollment, those on atorvastatin, and those on other statins. Patients will remain on study from enrollment until 1 year, disease relapse requires therapy, the physician withdraws the patient for safety reasons, or the patient withdraws for any reason.

Revision 2021. Since this trial was closed to accrual during the pandemic and new telemedicine practices and pandemic limitations are stifling accrual, this trial is being revised to enroll 50 patients with planned subgroups based on prior statin experience rather than the original 270 with 90 patients per statin cohort. This will still allow us to honor the patients already enrolled, learn something new, and also complete the trial in a reasonable amount of time under the new conditions. At the time of revision, there are 11 patients enrolled, and the first interim analyses as described in this revision allow the trial to continue.

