### **ii. Adverse Events**

Patients' adverse events will be recorded by CTCAE v 4.03 at baseline and throughout this trial and at 30 days after stopping the active treatment portion of this trial (1 year on PAVE).

iii. Use of other ED treatment after PAVE.

ED treatment medications prescribed during or upon leaving this trial will be collected at 18 months

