**D. Interim Analyses for Safety and Futility**

Interim analyses will begin after 10 patients have been enrolled. Monitoring will then be performed every 10 patients to ensure that patients are exhibiting reasonable toxicity and efficacy rates to continue with the trial. Patients who receive treatment less than 8 weeks will still be counted in toxicity and futility monitoring as long as they received at least 1 dose of the study drug. For patients already on statins, this means the patient must have started the combination. For patients who are starting on atorvastatin, patients will count as long as they received at least one dose of atorvastatin. If the trial can continue after 40 patients, then interim analyses will be complete. Adverse events will continue to be recorded and reported for all patients. If the toxicity or efficacy rates are noted to be different among the patient subgroups, the same stopping rules may be applied to any subgroup of concern to discontinue enrollment of that subgroup.

A Bayesian sequential monitoring design (Thall et al. 1995 and 1998) will be used to monitor the trial for toxicity and futility. Calculations were performed in MultcLean 2.1.

Toxicities will be monitored assuming a prior probability of toxicity following Beta(1,1) against a constant rate of 30% as the maximum acceptable toxicity rate. Trial limiting toxicities (TOX) are any grade 3 or higher toxicities at least possibly related to the study drug that occur in the first 8 weeks of therapy. The trial will be terminated if  $\text{Prob}(\text{TOX} > 0.30 \mid \text{data}) > 0.95$ . Following this rule, the trial will be terminated according to the table below once the first 10 patients have enrolled.

Similarly, efficacy will be monitored assuming a prior probability of response following Beta(0.33,0.67) against a constant rate of 33% as the minimum acceptable response rate. A patient will have a response if there is documented improvement at any time point on the trial. The trial will be terminated if  $\text{Prob}(\text{Response} < 0.33 \mid \text{data}) > 0.975$ . Following this rule, the trial will be terminated according to the following table once the first 10 patients have enrolled.

If there are this many patients treated who are evaluable (i.e., have TOX or completed the first 8 weeks without TOX for TOX, or have at least one IIEF result post-baseline for response)	10	20	30	40

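### Secondary objective ii is a rate of choosing other ED treatments after PAVE, but 11.0 E counts only men who drop out to start a prescription ED drug; among men who started PAVE, that count equals or understates the rate.

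*Combined protocol and SAP*

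**What the plan says.** Three statements bear on the same topic.

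- **Objective (3.0 B.ii):** "To report the rate of choosing other ED treatments after PAVE".
- **Endpoint iii (11.0 B):** "ED treatment medications prescribed during or upon leaving this trial will be collected at 18 months".
- **Analysis (11.0 E):** "the number of patients who drop out of the study to start an ED prescription medication will be reported".

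The last is the only sentence in 11.0 E on this subject. It names no denominator and does not refer to the 18-month data.

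Section 11.0 A gives four ways off study: reaching 1 year, relapse that needs therapy, and the two in "the physician withdraws the patient for safety reasons, or the patient withdraws for any reason". Section 8.0 adds detail on leaving for toxicity. For example, where a Grade 3 or higher toxicity cannot be assigned to one drug, 8.0 G.2 says to "stop all 3 drugs and the patient should be removed from the study"; 8.0 D to F contain removal rules for toxicity assigned to a single drug.

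Section 11.0 D supplies a usable definition of having started treatment. Men count in the monitoring "as long as they received at least 1 dose of the study drug". For men already on a statin this means that the combination was started; for men new to atorvastatin, one dose of atorvastatin is enough.

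**The concern.** The objective, the endpoint and the analysis describe three different quantities. The objective is a rate over all men who turn to another ED treatment. The endpoint is a set of prescriptions, gathered whether or not the man dropped out. The analysis is a count of men who left for one particular reason.

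A report that followed 11.0 E to the letter would not answer objective ii. It would leave out the men to whom the words after PAVE most naturally apply: those who finish the year and are then prescribed something else. The quantity matters to the trial's stated aim, since 11.0 A presents PAVE on the footing that "this combination may be a less expensive alternative for those patients who do benefit". How many men go on to other treatment is part of judging that, and the plan gathers data for it without saying that they will be analysed.

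**Working it through.** The plan states no figure for objective ii, so there is none to reproduce. The check is one of set inclusion, followed by simple arithmetic.

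**Step 1. Define the sets, among men who started PAVE.**
- A = men who drop out to start a prescription ED drug (11.0 E).
- B = men who choose another ED treatment after PAVE (3.0 B.ii).

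Every man in A has left PAVE and chosen another ED treatment, so he is also in B. Hence A is contained in B.

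**Step 2. Set the exit routes in 11.0 A against the 11.0 E count.**

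| Exit route | Prescribed ED treatment afterwards: counted in 11.0 E? |
|---|---|
| Completes 1 year | No, he has not dropped out |
| Relapse needing therapy | No, he left for another reason |
| Physician withdrawal for safety | No, he left for another reason |
| Patient withdrawal | Only if he withdrew to start a prescription ED drug |

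The count covers part of one route out of four.

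**Step 3. Test the narrow reading of endpoint iii.** If its wording excludes drugs first prescribed months after leaving, some later users fall outside the endpoint. A completer, or a man withdrawn for safety, who is prescribed a drug on leaving is still inside the endpoint and outside the 11.0 E count. The mismatch remains.

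**Step 4. Direction and size.** Let n be the number of men who started PAVE, D the size of A, and U the number in B but not in A.
- Figure from 11.0 E, put over n: D/n.
- Rate in objective ii: (D + U)/n.
- Gap: U/n, which is zero only if U = 0.

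With n = 50 (11.0 C, if all enrolled men start treatment), each omitted user is worth 1/50 = 2 percentage points.

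**Step 5. Illustration.** The documents give no values for D or U; those below are assumptions that show the range, with n = 50.

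| D | D/50 | Rate if U = 0 | U = 5 | U = 10 | U = 15 |
|---|---|---|---|---|---|
| 3 | 6% | 6% | 16% | 26% | 36% |
| 5 | 10% | 10% | 20% | 30% | 40% |
| 10 | 20% | 20% | 30% | 40% | 50% |

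**Step 6. The missing denominator.** The same count of 5 reads as 5/50 = 10%, 5/40 = 12.5% or 5/30 = 16.7%, according to how many men it is set against. This is a smaller matter than the narrow numerator.

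**The case against.** The strongest reply is that this is a wording slip in a descriptive secondary measure. Endpoint iii already calls for the wider data, enrolment is fixed at 50, and anyone can divide. Section 2.0 also says that cost and poor insurance cover limit use of the standard ED drugs, so few men may be omitted.

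Much of this stands. The gap may be small, and the prescribing data are planned. But dividing the count by 50 gives a rate of dropping out to start a prescription drug, which still leaves out completers. Endpoint iii specifies collection, not analysis.

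A reader might also infer more than the documents support:

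- **That the count can never exceed the objective's rate.** This holds only among men who started PAVE. The 11.0 E sentence has no such condition, so a man who enrolled, never started and left for an ED drug would be counted although he is not a case after PAVE.
- **That men prescribed an ED drug while still on PAVE are wrongly left out of the objective's rate.** Endpoint iii's text includes them; objective ii speaks of choice after PAVE. This is a disagreement between objective and endpoint, to be settled in the wording.
- **That the gap can be sized from the toxicity rates in the operating characteristics table.** The column headed "True Toxicity Rate" holds simulation inputs, for related events of Grade 3 or higher in the first 8 weeks. They are not forecasts, and they say nothing about later ED treatment. Nor does every safety stop lead to removal from the study: the liver enzyme and creatine kinase rules (8.0 D.1 and D.2) and the cardiovascular rule (8.0 G.4) stop drugs without stating it.
- **That the count would make PAVE look successful.** The measure has no comparator, threshold or decision rule, and low uptake could simply reflect cost.

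**Conclusion.** The point holds. The one analysis in 11.0 E on this topic gives a narrower quantity than objective ii and does not use the endpoint iii data. Among men who started PAVE, and on a common denominator, it equals the objective's rate only if no completer, and no man who left for another reason, goes on to another ED treatment; otherwise it is too low.

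The size is unknown: 2 percentage points for each omitted user if 50 men are treated. The direction rests on two assumptions, that the denominator is men who started PAVE and that men counted as leaving to start a drug did choose it.

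The primary analysis, the stopping rules and the sample size of 50 are not affected. The text should be corrected, but this does not threaten the trial, and the rate can be tabulated from data already due to be collected.

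**What to change.** Replace the sentence in 11.0 E with:

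*Among patients who started study treatment (as defined in 11.0 D), the proportion prescribed another ED treatment, from the endpoint iii data gathered at 18 months, will be given with its numerator, its denominator and the number of men lacking 18-month data. Treatment begun while on PAVE and treatment begun after stopping PAVE will be shown separately. Men who left the study in order to start a prescription ED drug will be shown as a subset.*

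Pointing to the 11.0 D definition matters, because it differs between men already on a statin and men new to atorvastatin.

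Then make objective ii and endpoint iii agree on two things: whether the scope is all other ED treatments or prescribed medications only, and whether the window is after PAVE, or during the trial and on leaving it.

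The cost is one sentence, a wording change and a little extra tabulation, with no more patients. If all ED treatments are chosen as the scope, one data item is added to the 18-month collection. The reported figure may be less favourable to PAVE. Some 18-month data will probably be missing for men who left early: the documents do not say that they are followed to that point, section 1.0 gives participation as 1 year, and Table 1 times its visits from the day all three drugs are first taken together. That is why the number without 18-month data should be reported beside the proportion.
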